#### **2.3.4 Study duration per subject**

For each subject, there is a planned duration of up to 109 weeks, as follows:

- Up to 5 weeks of Screening Period
- 48 weeks in the Open-Label Period
- 48 weeks in the Double-Blind Period

- An SFU Visit 10 weeks after last dose administration (Period 4).

Of note, the last dosing in the Double-Blind Period occurs at Week 94 so that the SFU of 10 weeks already includes 2 weeks from the Double-Blind Period hence leading to a duration of 109 weeks.

Subjects in UK will be contacted by a telephone call 22 weeks after the last dose of their study medication hence leading to a duration of 121 weeks.

For subjects who experience a flare during the Double-Blind Period, the study duration might be prolonged.

### **2.3.5       Planned number of subjects and sites**

Approximately 1250 subjects will be screened in order to enroll 750 subjects into Part A, where 210 subjects are expected to meet the sustained remission criteria and be eligible for randomization into Part B. The ASDAS scores will be closely monitored during Part A of the study to project the percentage of enrolled subjects likely to achieve sustained remission at the end of Part A. The enrollment will be adjusted accordingly in order to achieve the required number of 210 subjects in sustained clinical remission qualifying for Part B.

The end of the study is defined as the date of the last visit (SFU) of the last subject in the study. It is planned to enroll the subjects at approximately 95 sites.

The study will be conducted in North America, Western Europe, Eastern Europe and Asia.

### **2.4       Determination of sample size**

It is anticipated that approximately 210 subjects will be randomized in a 1:1:1 ratio to the CZP 200mg Q2W, CZP 200mg Q4W, and PBO treatment groups. The primary efficacy analysis is based on the proportion of subjects who do not experience a flare during Part B of the study. The proportion of subjects who do not experience a flare during Part B is assumed to be 80%, 75%, and 45% for the CZP 200mg Q2W, CZP 200mg Q4W, and PBO treatment groups, respectively. Given these assumptions, a sample size of 70 subjects per group provides 98% power to detect a significant difference between the CZP 200mg Q2W dose and PBO and 94% power to detect a significant difference between the CZP 200mg Q4W dose and PBO using a 2-sided significance level of 0.05.

Given that subjects enter Part B only if they have achieved sustained remission in Part A, it is necessary to estimate the number of subjects needed to enroll in Part A. It is assumed that approximately 28% of subjects enrolled in Part A will achieve sustained remission and qualify for Part B. This means that about 750 subjects will be enrolled in Part A in order to have 210 subjects who are randomized into Part B.

## **3           DATA ANALYSIS CONSIDERATIONS**

### **3.1       General presentation of summaries and analyses**

Statistical analysis and generation of tables, figures, and listings will be performed using SAS® Version 9.3 or higher.

Frequency tables (frequency counts and percentages) will be presented for categorical data. If there are missing values, either a missing category will be included in the display or the number of non-missing results will be used for calculations.

In case imputation was performed, summary statistics will not utilize the 'n' (number of available measurements). In addition, for the primary variables and selected outputs the 95% confidence interval (CI) based on the Exact Binomial distribution will be presented.

In general percentages will be calculated based on the utilized analysis set, however in case only subsets are affected, the N of the subset will be used as denominator.

Unless otherwise noted, all percentages will be displayed to 1 decimal place. No percentage will be displayed for zero counts, and no decimal will be presented when the percentage is 100%.

Continuous variables will be summarized with n (number of available measurements), arithmetic mean, standard deviation (SD), median, minimum, and maximum (with 25th and 75th percentiles where specified). For CZP plasma concentration levels and CRP observed values and ratio of post-Baseline over Baseline values the geometric mean and the corresponding coefficient of variation (CV) will be presented. The CV will be calculated as

$$CV = \sqrt{e^{std \ln^2} - 1} * 100$$

where "std ln" represents the standard deviation of the natural logarithm transformed parameter.

The mean, SD, and median will be displayed to 1 more decimal place than collected in the electronic Case Report Form (eCRF). Minimum and maximum values will be displayed to the same level of precision as collected in the eCRF. Unless otherwise specified, all statistical hypothesis tests will be 2-sided and the level of significance for all tests will be 0.05. P-values will be displayed to 3 decimal places.

The study design has three different periods: Part A, Part B and Escape Part. The outputs will be presented for each period. Summaries for Part A will be presented by axSpA subpopulation. Summaries for Part B will be presented by treatment group excluding any post-flare assessments in the subset of subjects experiencing a flare in Part B and start escape therapy. For the subset of subjects experiencing a flare in Part B and start escape therapy, separate summaries will be produced for the Escape Part.

## 3.2 General study level definitions

### 3.2.1 Bath Ankylosing Spondylitis Disease Activity Index (BASDAI)

The BASDAI is a validated self-reported instrument which consists of 6 horizontal NRSs, each with 10 units to measure the severity of the 5 major symptoms: fatigue, spinal pain, peripheral joint pain and swelling, enthesitis, and morning stiffness (both severity and duration) over the last week. To give each symptom equal weighting, the average of the 2 scores relating to morning stiffness is taken. The resulting 0 to 50 sum score is divided by 5 to give a final BASDAI score between 0 and 10, with lower scores indicating lower disease activity.

The BASDAI is calculated as follows:

$$BASDAI = \frac{Q1 + Q2 + Q3 + Q4 + \frac{Q5 + Q6}{2}}{5}$$

When calculating observed case value, following rules will be applied:

- [REDACTED]

- if 1 major symptom of the BASDAI is missing, the sum score of the remaining symptoms will be divided by the number of symptoms assessed
- If more than 1 major symptom is missing, the sum score will be set to missing. No imputation will be performed.

When performing last observation carried forward (LOCF) imputation, following rules will be applied:

- If more than one but not all components are missing at a visit, the previous value for the missing components will be carried forward to replace the missing components, assuming the previous values were from a post-baseline assessment and used to calculate the BASDAI score. If there are no previous post-baseline values available for any of the missing components to carry forward, the previous visit's total BASDAI score will be carried forward, assuming the previous visit was a post-baseline assessment. Otherwise the LOCF score is missing at that visit.
- If all components are missing at a visit, the previous visit's total BASDAI score will be carried forward, assuming the previous visit was a post-baseline assessment. Otherwise the LOCF score is missing at that visit.

The response variable BASDAI50 will be defined as an improvement (reduction) of at least 50% in the BASDAI compared to Baseline.

### **Fatigue item of the BASDAI**

Fatigue as a major symptom of ankylosing spondylitis (AS) can effectively be measured with single item questions such as the BASDAI item. This item has shown moderate to good reliability and responsiveness. The fatigue item score will range from 0 to 10.

### **3.2.2 ASAS20, ASAS40, ASAS5/6 response, and ASAS Partial Remission**

The ASAS20 is defined as an improvement (decrease) of  $\geq 20\%$  and absolute improvement (decrease) of  $\geq 1$  unit on a 0 to 10 NRS in at least 3 out of 4 domains as follows:

- PtGADA (see Section 3.2.10)
- Pain assessment (total spinal pain NRS score)
- Function (represented by BASFI, Section 3.2.3)
- Inflammation (the mean of the BASDAI questions 5 and 6, [see Section 3.2.1] concerning morning stiffness intensity and duration)

and absence of deterioration in the potential remaining domain (deterioration is defined as a relative worsening (increase) of  $\geq 20\%$  and absolute worsening (increase) of  $\geq 1$  unit).

The ASAS40 is defined as an improvement (decrease) of  $\geq 40\%$  and absolute improvement (decrease)  $\geq 2$  units on a 0 to 10 NRS in at least 3 out of 4 domains and no worsening (increase) at all in the remaining domain.

The ASAS5/6 response is defined as an improvement of  $\geq 20\%$  in at least 5 out of 6 domains comprised of the 4 domains above plus additional domains of spinal mobility (ie, BASMI, lateral lumbar flexion), and CRP. The lateral lumbar flexion value is taken as the mean of left and right assessment values and improvement is a  $\geq 20\%$  increase. Improvement in CRP is a  $\geq 20\%$  decrease. If the CRP value is below the lower limit of quantification (LLOQ), then it will be imputed as the midpoint between 0 and the LLOQ.

The ASAS PR response is defined as a score of  $\leq 2$  units on a 0 to 10 NRS in each of the 4 domains listed above for ASAS20.

When calculating observed case response status for ASAS20, ASAS40, ASAS5/6 and ASAS PR, following rules will be applied:

- If 1 of the 2 morning stiffness measurements (ie, questions 5 and 6 of BASDAI questionnaire) is missing, the other one will be used for the inflammation calculation.
- If one or more components are missing at a visit, the response status will be treated as missing at that visit. No imputation will be performed. Subjects will not be handled as non-responder.

When performing non-responder imputation (NRI) for ASAS20, ASAS40, ASAS5/6 and ASAS PR, following rules will be applied:

- If some but not all components are missing at a visit, the previous value for the missing components will be carried forward to replace the missing values, assuming the previous values were from a post-baseline assessment. The response status will then be assessed. If there is no previous post-baseline value available to carry forward for any of the missing components, a 0 unit improvement value and 0% improvement value will be imputed for the missing components. The response status will then be assessed.
- If all components are missing at a visit, then the subject will be considered a non-responder at that visit.

### **3.2.3 Bath Ankylosing Spondylitis Functional Index (BASFI)**

The BASFI comprises 10 items relating to the past week. The NRS version will be used for the answering options of each item on a scale of 0 (“Easy”) to 10 (“Impossible”). The BASFI is the mean of the 10 scores such that the total score ranges from 0 to 10, with lower scores indicating better physical function.

In case of missing answers to 1 or 2 of the single items within the BASFI questionnaire, the BASFI score will be calculated by imputing missing items with the mean of the completed items. Then, the BASFI score will be calculated as described above. If more than 2 of the items are missing, the BASFI score will be left missing.

### **3.2.4 MRI assessments**

Magnetic resonance imaging of the spine and sacroiliac joints will be performed at Screening, Week 48, Week 96, or Withdrawal Visit if the previous MRI was performed more than 12 weeks prior to withdrawal. In the Escape Part it will be also performed at Escape Week 0 and 12. MRI will be assessed centrally and scoring will be done according to the imaging charter by independent readers, who are blinded to both the order of the scans and to the treatment group,

using a previously reported scoring system. A single reader assessment will be performed for Week 0 and Week 48 in the MRI scores for all subjects that entered Part A and have at least one post-baseline scan. A double reader assessment will be performed for subjects entering Part B. The analysis will use the average of the scores from the 2 independent reviewers. If the two readers disagree a third reviewer who is not one of the two reviewers will perform adjudication by providing a third independent review. Whenever an adjudication is present the average score across all 3 reviewers will be used for analysis. Two different MRI scores will be used for analysis (SPARCC, Berlin modification of the ASspiMRI-a).

The SPARCC scoring method for lesions found on the MRI is based on an abnormal increased signal on the short-tau-inversion recovery (STIR) sequence, representing bone marrow edema (defined as an increased signal in bone marrow on a T2-weighted sequence, reflecting an increased concentration of “free water” related to a bone lesion). Each SIJ is divided into 4 quadrants and will be assessed for left and right: upper iliac, lower iliac, upper sacral, and lower sacral. The presence of increased signal on STIR in each of these 4 quadrants are scored on a dichotomous basis, where 1 = increased signal and 0 = normal signal. Joints that include a lesion exhibiting intense signal are each given an additional score of 1 per slice that demonstrated this feature. Similarly, each joint that included a lesion demonstrating continuous increased signal of depth greater or equal 1 cm from the articular surface is also given an additional score of 1. The scoring is repeated in each of 6 consecutive coronal slices. Total SIJ SPARCC scores can range from 0 to 72.

The Berlin modification of the ASspiMRI-a is a scoring system with a concentration on STIR sequences without other fat saturation techniques. This scoring method quantifies active changes in 23 vertebral units (VU) of the spine (from C2 to S1) or 24 VUs if a transitional vertebra is present. If a transitional vertebra is present, L5/L6 and L6/SI will be assessed instead of L5/SI. A VU is defined as the region between 2 virtual lines through the middle of each vertebra. Active inflammation is scored by grading the degree of bone marrow edema from 0 to 3 in 1 dimension on 1 or more consecutive slices that represent the highest level of inflammation in a particular VU.

Total spine ASspiMRI-a score in the Berlin modification can range from 0 to 69. This score will increase if there are transitional vertebrae.

The following imputation rules should be used for calculating the total for both SIJ SPARCC scores and spine ASspiMRI-a score in the Berlin modification:

- If all scores are not applicable (NA) at a visit, the imputed total is blank for that visit.
- Treat NA as 0 when computing the total score.
- Carry the NA score from the Baseline Visit forward to all post-Baseline visits unless all scores at Baseline are NA.
- Carry the numeric score from the last visit with non-NA score forward if a score is NA at a post-Baseline visit (unless all scores are NA post-Baseline).
- If ALL the Baseline scores are NA, then do not carry forward the Baseline scores. Treat the subsequent visit as a surrogate Baseline.

For MRI the relative day after scheduled MRI visit will be calculated.

In case of out of window images/scores regarding the visit date, the following rules will apply:

- MRI assessments assigned to Baseline:
  - If Baseline MRI was performed from Screening up to 2 weeks after Baseline it will be assigned to Baseline, if beyond it will not be used.
- MRI assessments assigned to Week 48:
  - If Week 48 MRI was performed  $\pm 2$  weeks around the Week 48 Visit, it will be assigned to Week 48, otherwise Week 48 will be treated as missing.
- MRI assessments assigned to Week 96:
  - If Week 96 MRI was performed  $\pm 2$  weeks around the Week 96 Visit, it will be assigned to Week 96, otherwise Week 96 will be treated as missing.

In subjects experiencing a flare in Part B, following rules will apply:

- MRI assessments assigned to Escape Week 0:
  - If Escape Week 0 MRI was performed  $\pm 2$  weeks around the Escape Week 0 Visit, it will be assigned to Escape Week 0, otherwise Escape Week 0 will be treated as missing.
- MRI assessments assigned to Escape Week 12:
  - If Escape Week 12 MRI was performed  $\pm 2$  weeks around the Escape Week 12 Visit, it will be assigned to Escape Week 12, otherwise Escape Week 12 will be treated as missing.

In case a MRI is performed at a premature Withdrawal Visit, it will be assigned to what would have been the next scheduled visit with a MRI assessment. The MRI will be used for summaries if it was performed  $\pm 2$  weeks around the scheduled visit it is assigned to.

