The LOCF imputation will be done whether the data is missing, the subject discontinued prior to the time point assessed, or the data is considered missing due to start of escape treatment.

Unless otherwise stated, the following guidelines apply for the LOCF analyses:

- For missing post-baseline Part A assessments, only carry forward earlier Part A post-Baseline values. Screening and Part A Baseline values do not get carried forward to the Part A post-Baseline visits.
- For missing post Week 48 Part B assessments,
  - if the subject did not experience a flare in Part B, only carry forward earlier Part B post-Week 48 values,
  - if the subject experienced a flare in Part B, the assessment at Escape week 0 will be treated as the last assessment in Part B prior to escape treatment. For any missing post 48 Part B assessments up to the week of flare (the later visit if flare was based on 2 visits), carry forward earlier Part B post-Week 48 values. Assessments whilst on escape treatment are not to be used, therefore the assessment at Escape week 0 will be carried forward for all subsequent visits until Week 96. E.g if the subject experienced a flare at week 72 then the Escape Week 0 assessment will be carried forward for the assessments after week 72 in Part B (76, 80, 84, 88, 92 and 96)

- Week 48 values do not get carried forward to the Part B post-Baseline visits.
- Assessments during escape treatment will not be carried forward.
- The following continuous endpoints in Part B will be compared between treatment groups using a mixed model for repeated measures (MMRM). The pattern of missingness for these variables is assumed to be MAR. Subjects who enter Part B will have already demonstrated sustained remission through 48 weeks on CZP 200mg Q2W. Many of these subjects will be randomized to receive placebo and will, therefore, be more likely to experience a flare. Post-flare data for subjects experiencing a flare (in any treatment group) will be treated as missing for the MMRM analysis. It is further assumed that most subjects who discontinue at this late stage in the study (i.e. during Part B) will do so as a result of reduced efficacy. Therefore, missing efficacy data due to either flare or study treatment discontinuation should be dependent on the observed efficacy scores, but independent of unobserved data. For the following continuous endpoints in Part B, imputation of missing data will be performed using the MMRM approach:
  - ASDAS
  - BASDAI

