The changes from Part B Baseline in SIJ SPARCC and spine ASspiMRI-a in the Berlin modification scores at Week 96 will be compared between treatment groups using an analysis of covariance (ANCOVA) model. The model will include Part B Baseline score, treatment group, region, and mNY classification. Summary tables will present the adjusted means for PBO and the CZP doses, the respective differences to PBO, the corresponding p-values, and 95% CIs. This analysis will be performed using observed case data only.

These summary statistics will be repeated for Part A Baseline and the model includes Part A Baseline score, treatment group, region, and mNY classification.

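### The location-level NA rules for MRI are tied to the Week 0 scan and cross study phases, so change from Part B Baseline loses observed scores and takes in scores from another phase

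*SAP*

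**What the plan says.** SAP section 3.2.4 schedules the scans: "Magnetic resonance imaging of the spine and sacroiliac joints will be performed at Screening, Week 48, Week 96, or Withdrawal Visit", with further scans at Escape Weeks 0 and 12. It then gives imputation rules for both total scores:

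- "If all scores are not applicable (NA) at a visit, the imputed total is blank for that visit". The remaining rules therefore act on single locations, not on whole scans.
- "Treat NA as 0 when computing the total score". There is no rescaling.
- "Carry the NA score from the Baseline Visit forward to all post-Baseline visits unless all scores at Baseline are NA". The rule makes no exception for a location that a later scan did score.
- A further rule covers locations that become NA afterwards: "Carry the numeric score from the last visit with non-NA score forward if a score is NA at a post-Baseline visit". No limit is set at Week 48 or at the start of escape.
- If every Baseline score is NA, the next visit serves as a surrogate Baseline.

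Baseline in this section is the pre-treatment scan: "If Baseline MRI was performed from Screening up to 2 weeks after Baseline it will be assigned to Baseline". Week 48 has its own, separate window.

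Section 8.2.2.2 fits an ANCOVA to the change in each MRI score from Part B Baseline to Week 96 and says "This analysis will be performed using observed case data only". It repeats the analysis for Part A Baseline. For subjects who flare, sections 2.2.1.2.3 and 8.2.3.1 add descriptive changes from Part B Baseline and Flare Baseline.

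**The concern.** Change from Part B Baseline uses two scans, Week 48 and Week 96. The Week 0 scan has no role in it, yet the rules bring that scan in twice.

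1. A location NA at Week 0 is set to 0 at Weeks 48 and 96, even when both scans scored it.
2. A location NA at Week 48 takes its pre-CZP score, so the Part B Baseline can contain untreated inflammation.

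In addition, a location NA at Week 96 takes its last earlier score. In a subject without escape scans this is the Week 48 score on open-label CZP, which then stands in for the randomized phase. The same happens one step later in escape: a location NA at Escape Week 0 takes an earlier score as its Flare Baseline.

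At stake is a between-arm MRI comparison that supports a named secondary objective, inflammatory change over time.

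**Working it through.** **Plan's own figures.** SPARCC: (4 quadrants × 2 sides + 2 intensity + 2 depth) × 6 slices = 72. Berlin spine score: 23 units × 3 = 69. Both agree with section 3.2.4.

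**Rules applied literally to one spine unit (0 to 3), other units 0.** The examples assume that all readers agree; if only one of two averaged readers records NA, the effect halves.

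| Week 0, 48, 96 | Week 48–96 change, observed | Under the SAP rules |
|---|---|---|
| NA, 0, 3 | +3 | 0 |
| 3, NA, 0 | not observed | −3 |
| 3, 0, NA | not observed | 0 |
| 3, NA, NA | not observed | 0 |

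Each unit NA at Week 0 lowers the attainable maximum by 3 at every visit (69 to 66 for one unit). The surrogate-Baseline rule also gives an odd ordering: a subject with 23 of 23 units NA at Week 0 keeps all units later, while one with 22 of 23 NA loses 22.

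**Effect on the arm difference.** Let a location be NA at random with probability m at each scan, independently. It contributes to the arm difference only if scored at Week 0 (otherwise masked) and at Week 96 (otherwise the change is 0). A carried Week 0 score at Week 48 has the same expectation in all arms and cancels. So the retained share is (1 − m)(1 − m) = (1 − m)².

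The SAP gives neither an NA rate nor lesion rates, so all of the following are assumptions: 23 units; mean lesion probability per unit 0.08 at Week 0, 0.015 at Week 48, and 0.05 (PBO) or 0.015 (CZP) at Week 96; grades 1 to 3 equally likely (mean 2); lesion rates varying between subjects. The true difference is 23 × 2 × (0.05 − 0.015) = 1.61. Simulation with 60,000 subjects per arm gave:

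| m | Full data | SAP rules | Ratio | (1 − m)² | Prorated over units scored at Weeks 48 and 96 |
|---|---|---|---|---|---|
| 2% | 1.62 | 1.56 | 0.96 | 0.960 | 1.63 |
| 5% | 1.61 | 1.45 | 0.90 | 0.903 | 1.62 |
| 10% | 1.60 | 1.30 | 0.81 | 0.810 | 1.60 |
| 20% | 1.63 | 1.02 | 0.63 | 0.640 | 1.62 |

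**Shift within each arm.** The Week 0 to Week 48 carry lowers the mean change by 23 × (1 − m)² × m × 2 × (0.08 − 0.015). At m = 10% this is 23 × 0.81 × 0.10 × 0.13 = 0.24. In the simulation the CZP mean change moved from −0.004 to −0.246, which agrees. The shift is common to the arms.

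**The case against.** **NA may be structural.** The plan writes not applicable, not unreadable; reads follow an imaging charter that is not at hand; and the section itself names transitional vertebrae. A structurally absent location would be NA at every scan, and masking would then remove nothing. This limits the likely size but does not answer the point: the rule that fills a post-Baseline NA from an earlier numeric score presupposes that a location can be scored at one visit and NA at the next.

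**The listed secondary variable is another one.** Section 2.2.1.2.2 lists change from Part A Baseline at Week 96. There, masking keeps the locations like for like with the Week 0 scan and is acceptable. This stands. The point concerns change from Part B Baseline, which section 8.2.2.2 nevertheless analyses first.

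**A reader might infer a contradiction with section 4.2**, which says "Week 48 values do not get carried forward to the Part B post-Baseline visits". That sentence belongs to the guidelines for LOCF analyses, which hold unless otherwise stated. MRI is not among the LOCF endpoints, and section 3.2.4 states its own rule. There is no formal contradiction.

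**A reader might infer that observed case is a mislabel.** Elsewhere the SAP repairs items under that label: the observed-case BASDAI tolerates one missing symptom. The label alone proves no error, although here a score that was read can be overwritten.

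**A reader might infer that the rules hide relapse, mostly on PBO.** The text does not show this. Masking and the Week 48 fill act in all arms. Flared subjects may have escape scans, which would then be the last numeric scans, and it is unclear whether their later scans enter the ANCOVA: section 3.1 excludes post-flare assessments from Part B summaries, while section 4.2 exempts radiographic data.

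**Conclusion.** The point holds for change from Part B Baseline, and likewise for change from Flare Baseline. The rules can replace an observed +3 in a unit by 0, and can create a change of −3 from a pre-treatment score. The consequences are discarded data, added error and a tendency towards a smaller CZP–PBO difference. No arm is favoured.

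The overall size is unknown because no NA rate is given. The retained share of 96% at a 2% rate to 63% at 20% rests on assumed lesion rates and on NA being random and independent between scans. It would be a stretch to cite a subject with four units NA at Week 0 losing 4 × 3 = 12 of 69 points: that needs all four units scored later, at the top grade, and is a worst case. The p-values concerned are nominal (section 8.2.2), and the primary flare endpoint, which rests on ASDAS, is untouched. The reading of Baseline as Week 0 follows from the scan windows. If a contrast-specific baseline was intended, the plan need only say so and limit the carry. The correction is cheap and worth making.

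**What to change.** In section 3.2.4, state the NA rules per contrast:

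- **Change from Part A Baseline:** keep the masking by the Week 0 scan.
- **Change from Part B Baseline:** use Week 48 as the baseline scan, so that only locations scored there count.
- **Change from Flare Baseline:** use Escape Week 0 in the same way.
- For the Part B and Flare Baseline contrasts, carry no location score across Week 48 or Escape Week 0, and base the change on locations scored at both visits.
- Keep the present rule as a sensitivity analysis labelled as imputed.

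Prorating to the full number of locations is optional. If NA rates are m0, m48 and m96, the present rule keeps (1 − m0)(1 − m96) of the difference and the unscaled fix keeps (1 − m48)(1 − m96). With equal rates these are the same, so without scaling the gain is that every counted change was observed and the false shift disappears. Prorating also restores the scale, as the joint counts in section 3.2.13 do, but it is itself an imputation. It needs a minimum number of scored locations and a rule for the SPARCC depth and intensity points.

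The cost is SAP wording and programming on existing reads. The downside is that a subject's Week 48 total may differ between the Part A Baseline and Part B Baseline tables, which a footnote can explain.

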### **2.3.1 Part A**

Part A consists of two study periods.

**Period 1** (Screening Period): Up to 5 Weeks before Baseline

**Period 2** (Open-Label Period): Week 0 (Baseline) to Week 48

Within Period 2, eligible subjects will receive 3 loading doses of CZP 400mg at Weeks 0, 2, and 4 followed by CZP 200mg Q2W.

All subjects who have not achieved sustained remission at the end of Period 2 (Week 48) will be discontinued from the study and treated at the discretion of their physician. Those subjects who discontinue prematurely from the study for any reason will be treated at the discretion of their physician.

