### **3.4 Definition of Baseline values**

The study baseline value for a subject noted “Part A Baseline” will be defined as the latest measurement for that subject up to and including the day of administration of first study medication in Part A, unless otherwise stated. If a Part A Baseline measurement is missing or not collected, and a Screening value is available, the Screening value will be utilized as Part A Baseline instead. If no measurement is available prior to receiving study medication in Part A, the Part A Baseline value is treated as missing.

For subjects randomized into Part B, a “Part B Baseline” will be defined as the latest measurement for that subject up to and including the day of randomization, unless otherwise stated. If a Part B Baseline measurement is missing or not collected, and a post-Baseline Part A value is available, the post-Baseline Part A value will be utilized as Part B Baseline instead. If no post-Baseline Part A measurement is available prior to randomization, the Part B Baseline value is treated as missing.

For subjects experiencing a flare in Part B, a “Flare Baseline” will be defined as the latest measurement for that subject up to and including the day of administration of first escape treatment in Part B, unless otherwise stated. If a Flare Baseline measurement is missing or not collected, and a post-Baseline Part B value is available, the post-Baseline Part B value will be utilized as Flare Baseline instead. If no post-Baseline Part B measurement is available prior to receiving study medication in Escape Part, the Flare Baseline value is treated as missing. If a subject does not receive study medication in Escape Part, the last available post-Baseline Part B measurement will be used as Flare Baseline.

For each baseline definition, if there is evidence that measurements taken on the same day as administration of first study medication (in Part A/Part B) or first escape treatment (for subjects experiencing a flare in Part B) were actually taken after this administration, then only values strictly prior to that date (including screening assessment visits if appropriate) will be used for that subject. When the date of first dose is derived, it should be based on the first injection of study treatment, regardless of whether it is an active treatment.

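### On a plain reading, an all-NA baseline MRI is replaced by the on-treatment Week 48 scan, so change from Part A Baseline is no longer change from before treatment

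*SAP*

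**What the plan says.** SAP Section 3.2.4 schedules MRI so that it "will be performed at Screening, Week 48, Week 96, or Withdrawal Visit", with further scans at Escape Weeks 0 and 12 after a flare. It then lists imputation rules for calculating the total SIJ SPARCC and spine ASspiMRI-a scores. The first rule leaves the total blank at any visit where all scores are NA. The last rule reads: "If ALL the Baseline scores are NA, then do not carry forward the Baseline scores. Treat the subsequent visit as a surrogate Baseline".

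The same section limits how late a baseline scan may be. A scan done "from Screening up to 2 weeks after Baseline it will be assigned to Baseline, if beyond it will not be used". A scan from a premature withdrawal visit is handled separately: "it will be assigned to what would have been the next scheduled visit with a MRI assessment". It is used in summaries only if it lies within two weeks of that scheduled visit.

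Section 3.4 gives the general rule: "If no measurement is available prior to receiving study medication in Part A, the Part A Baseline value is treated as missing". The Part A Baseline definition there yields where the SAP states otherwise. The section ends by sending baselines that cannot be derived to the data evaluation meeting before database lock, where a substitute value is to be chosen.

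Change from Part A Baseline in the two MRI scores is a secondary variable at Week 96 (Section 2.2.1.2.2). It is summarised by visit in Part A (Section 8.3.1.4). In Part B it is analysed as a repeat of the Part B Baseline ANCOVA, with Part A Baseline score as covariate (Section 8.2.2.2).

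**The concern.** No scan is scheduled between Screening and Week 48, so the visit after an all-NA Screening scan is Week 48. By then every Part A subject has been on active drug: "eligible subjects will receive 3 loading doses of CZP 400mg at Weeks 0, 2, and 4 followed by CZP 200mg Q2W". A score taken at that point cannot serve as a pre-treatment reference. Used as one, it removes the subject's whole Part A response from the change score. The mean change from Part A Baseline then mixes two quantities, change since before treatment and change since the end of Part A, under one label.

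The SAP also gives three different answers for the same subject. The baseline is the Week 48 score under Section 3.2.4, missing under the general rule in Section 3.4, or a value chosen at the data evaluation meeting under the last paragraph of Section 3.4. Which one is used would depend on the paragraph the programmer follows.

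**Working it through.** The SAP states no figure on this point, so there is none to reproduce. The check follows the rule through the schedule and then illustrates its effect.

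**Which scan becomes the surrogate**
1. Scheduled scans are at Screening, Week 48 and Week 96 (Section 3.2.4).
2. A Part A withdrawal scan is assigned to Week 48 and is usable only within two weeks of it.
3. A scan later than two weeks after Baseline is not accepted as a baseline scan.
4. The first usable scan after an all-NA Screening scan is therefore at about Week 48, the end of the 48-week Open-Label Period (Sections 2.3.1 and 2.3.4).

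**What each rule gives for that subject**

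| Quantity | Surrogate rule, plain reading | Section 3.4 general rule |
|---|---|---|
| Part A Baseline | Week 48 score | missing |
| Change at Week 48 | Week 48 - Week 48 = 0, or undefined | missing |
| Change at Week 96 | Week 96 - Week 48 | missing |
| ANCOVA covariate | on-treatment score | subject not in the model |

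In the left-hand column, the Week 96 change is the change from Part B Baseline under another label.

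**Illustration with assumed scores**

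Take scores of 10 at Screening, 2 at Week 48 and 3 at Week 96. None of these comes from the SAP.
- Week 48 change: true 2 - 10 = -8; with the surrogate 2 - 2 = 0.
- Week 96 change: true 3 - 10 = -7; with the surrogate 3 - 2 = +1.

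Let k be the share of subjects with an all-NA baseline scan. The SAP does not give k, so a range of 1% to 10% is assumed.
- Mean Week 48 change, if the zeros are counted: (1 - k) × (-8).
- Mean Week 96 change: (1 - k) × (-7) + k × (+1).

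| k | Mean change, Week 48 (true -8.0) | Mean change, Week 96 (true -7.0) |
|---|---|---|
| 1% | -7.92 | -6.92 |
| 5% | -7.60 | -6.60 |
| 10% | -7.20 | -6.20 |

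Both means move by k times the Part A improvement, here k × 8. If affected subjects are set to missing instead, the illustrated means stay at -8.0 and -7.0.

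**The case against.** The strongest reply is that the sentence was never meant to define a baseline for change scores. It closes a list of rules for building totals from item scores. An earlier rule in that list already blanks an all-NA total, and another carries the baseline NA pattern forward except when every baseline score is NA. On that view the sentence only completes the exception: with no baseline pattern to carry, start from the next visit. The Part A Baseline total stays blank and the change stays missing. This reading is plausible, and it is why the point is about wording that permits a wrong result, not about a settled error. But the first half of the rule already stops the carry-forward. The second half adds a surrogate baseline, and nothing confines it to item-level use.

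A second reply is that Section 3.4 gives way where the SAP states otherwise, so there is no formal contradiction. That settles which rule has precedence. It does not make a score after 48 weeks of treatment a valid pre-treatment value. The two-week window is written for late baseline scans, not all-NA ones, so the tension there lies in purpose more than in wording.

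Third, scoring follows an imaging charter that is not at hand and may define NA and the surrogate more narrowly. If so, the SAP should say the same.

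A reader might also infer that an all-NA Week 48 scan would turn Week 96 or Escape Week 0 into the Part B Baseline and hide worsening after withdrawal. The SAP does not support that. Section 3.2.4 treats Baseline and Week 48 as separate visits, and for a missing Part B Baseline Section 3.4 looks back to an earlier Part A value, never forward.

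**Conclusion.** The concern holds for Part A Baseline. As written, Section 3.2.4 allows an on-treatment Week 48 score to stand as the pre-treatment reference for a secondary MRI variable, and this does not fit the SAP's other baseline rules.

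The impact is probably small. Only subjects whose baseline scores are all NA are affected, and the SAP gives no count. The shifts of 0.08 to 0.80 points shown above rest on assumed scores and an assumed share of 1% to 10%. The primary flare endpoint does not use MRI. The lead MRI comparison uses change from Part B Baseline, for which Week 48 is the proper reference.

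A reader might infer that the treatment comparison is biased. That is not shown. Whether the Screening scan is all NA is fixed before randomisation, the surrogate scan is taken at about the end of Part A, and the rule is the same in every arm. What suffers is the meaning and size of the within-group means, and the labelling of the change score. Nor does the rule expressly reach scans that were not done or fell outside the window; its trigger is that all scores are NA.

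**What to change.** In Section 3.2.4, delete the surrogate sentence, or limit it expressly to the item-level carry-forward of NA and numeric scores used in calculating totals. Add that when all scores of the Screening scan are NA:
- the Part A Baseline MRI total and any change from it are missing;
- the substitution at the data evaluation meeting described at the end of Section 3.4 does not apply. Without this, deleting the surrogate sentence would not by itself guarantee a missing baseline;
- the subject's actual scores and change from Part B Baseline are kept.

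The cost is a sentence or two in the SAP. The downside is that a few subjects leave the change score against Part A Baseline and the ANCOVA based on it.
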